Attachment 3. Protocol CXAD Hepatic Monitoring Tests for Treatment-Emergent Abnormality

Details for hepatic monitoring depend upon the severity and persistence of observed laboratory test abnormalities. To ensure patient safety and comply with regulatory guidance, the investigator is to consult with the Lilly CRP or designee regarding collection of specific recommended clinical information and follow-up laboratory tests.

Selected tests may be obtained in the event of a treatment-emergent hepatic abnormality and may be required in follow-up with patients in consultation with the Lilly CRP or designee.

Hepatic Monitoring Tests

Hepatic Hematology^a

Hemoglobin
Hematocrit
RBC
WBC
Neutrophils, segmented
Lymphocytes
Monocytes
Eosinophils
Basophils
Platelets

Hepatic Chemistry^a

Total bilirubin
Direct bilirubin
Alkaline phosphatase
ALT
AST
GGT
CPK

Haptoglobin^a

Hepatic Coagulation^a

Activated partial thromboplastin time
Prothrombin Time, INR

Hepatic Serologies^{a,b}

Hepatitis A antibody, total
Hepatitis A antibody, IgM
Hepatitis B surface antigen
Hepatitis B surface antibody
Hepatitis B Core antibody
Hepatitis C antibody
Hepatitis E antibody, IgG
Hepatitis E antibody, IgM

Anti-Actin antibody

Anti-nuclear antibody^a

Anti-smooth muscle antibody^a

Abbreviations: ALT = alanine aminotransferase; AST = aspartate aminotransferase; CPK = creatine phosphokinase; GGT = gamma glutamyl transferase; Ig = immunoglobulin; INR = international normalized ratio; RBC = red blood cells; WBC = white blood cells.

^a Assayed by Lilly-designated laboratory.

^b Reflex/confirmation dependent on regulatory requirements and/or testing availability.

Attachment 4. Protocol CXAD Pharmacokinetic, Pharmacodynamic, Immunogenicity, and Biomarker Sampling Schedule

Pharmacokinetic (PK) samples will be collected for both LY2510924 and durvalumab and immunogenicity (IK) samples will be collected for durvalumab only. Predose sample for LY2510924 should be drawn as close as possible prior to the subcutaneous (SQ) injection of LY2510924, and that for durvalumab should be drawn as close as possible prior to start of durvalumab infusion (but can be drawn up to 1 hour or 60 minutes prior to the start of infusion). All post-dose blood draws for LY2510924 PK should be drawn in the preferred time windows listed in the table below. Exact clock reading for the time of blood draw should be recorded. While best effort should be done to draw the blood sample within the time window provided, it is more important to ensure that the predose sample for LY2510924 and durvalumab is actually collected before the administration of SQ injection and start of infusion, respectively, and post-end of infusion sample for durvalumab should be collected after the infusion has actually completed. It is also equally important to record actual date and time of blood collection for PK/IK sample on the Requisition Form after drawing the sample. Sample collection for PK/IK must be from the opposite arm to that used for study drug infusion. If drug was administered via a central venous catheter, the sample collection should be from a different site.

In addition, if a patient experiences an IRR, blood samples for anti-durvalumab antibody and PK should be drawn, with no more than 15 minutes' time difference between PK and IK samples. Samples will be taken at the following time points: (1) as soon as possible after the onset of the IRR, (2) at the resolution of the IRR, and (3) 30 days after the IRR.

Pharmacokinetic, Pharmacodynamic, and Biomarker Sampling Schedule

Cycle	Day	PK Sampling Time for LY25109 24 ^a	PK Sampling Time for Durvalumab	Durvalumab Immunogenicity	Blood for Pharmacogenetics	Tailoring and Pharmacodynamic Biomarker			
						Plasma for Exploratory Research	Serum for Exploratory Research	Whole Blood for Immunophenotyping Including CD34+ Counts ^c and Other Exploratory Research	Tissue for PD-L1 and Exploratory Research
—	≤7 days				X			X	
1	1	Predose ^b				X	X	X	X (Core or excisional biopsy of a tumor lesion or a recent biopsy defined by ≤3 years since last documented progression of disease)
1	1	0.5 hr +/- 15 min	10 min after end of infusion (+/-5 min)						
1	1	2 hr +/- 30 min						X	
1	1	4 hr +/- 30 min					X		
1	1	6 hr +/- 30 min							
1	1	8 hr +/- 30 min							
1	2	24-30 hr post Day 1 dose ^b					X	X	
1	15	Predose ^b					X	X	

Cycle	Day	PK Sampling Time for LY25109 24 ^a	PK Sampling Time for Durvalumab	Durvalumab Immunogenicity	Blood for Pharmacogenetics	Tailoring and Pharmacodynamic Biomarker			
						Plasma for Exploratory Research	Serum for Exploratory Research	Whole Blood for Immunophenotyping Including CD34+ Counts ^c and Other Exploratory Research	Tissue for PD-L1 and Exploratory Research
1	15	0.5hr +/- 15 min							
1	15	2 hr +/- 30 min						X	
1	15	4 hr +/- 30 min					X		
1	15	6 hr +/- 30 min							
1	15	8 hr +/- 30 min							
1	16	24-30 hr post Day 15 dose ^b					X	X	
2	1	Predose ^b	Predose (before start of infusion)	X		X	X	X	X (On-treatment sample (Cycle 2 Day 7 ±7 days): mandatory for ovarian expansion arm (Phase 1b), optional in Phase 1a and pancreatic expansion arm in Phase 1b)
2	1	0.5 hr +/- 15 min							
2	1	4 hr +/- 30 min					X		
3	1	Predose ^b	Predose (before start			X	X	X	

Cycle	Day	PK Sampling Time for LY2510924 ^a	PK Sampling Time for Durvalumab	Durvalumab Immunogenicity	Blood for Pharmacogenetics	Tailoring and Pharmacodynamic Biomarker			
						Plasma for Exploratory Research	Serum for Exploratory Research	Whole Blood for Immunophenotyping Including CD34+ Counts ^c and Other Exploratory Research	Tissue for PD-L1 and Exploratory Research
			of infusion)						
4	1	Predose ^b	Predose (before start of infusion)	X			X	X	
4	1	0.5-4 hr	10 min after end of infusion (+/-5 min)						
6	1	Predose ^b	Predose (before start of infusion)						
30 days post t/ment						X	X		
90 days post-t/ment			Anytime	X					

Abbreviations: EDTA = ethylenediaminetetraacetic; hr = hour; min = minute; PD-L1 = programmed cell death ligand 1; PK = pharmacokinetic; t/ment = treatment.

^a Samples of approximately 5 mL of whole blood will be drawn into EDTA tubes for measurement of LY2510924 in plasma.

^b Patients should be instructed ahead of time that LY2510924 should be taken at the clinic.

^c Includes CD34+ counts, absolute neutrophil count (ANC), absolute lymphocyte count (ALC).

Attachment 5. Protocol CXAD Data Sharing and Sample Testing Schedule

Data Sharing and Sample Testing Schedule

Study Procedures	Shared between the Two Parties	Not Shared	Timing to provide item (data/sample, etc.)	Party to Analyze Data/Sample
Clinical/oncologic history	X		Early Results Memo	Lilly
Vital signs/weight	X		Early Results Memo	Lilly
Physical examinations	X		Early Results Memo	Lilly
ECOG Performance Status	X		Early Results Memo	Lilly
12-Lead ECG 7	X		Early Results Memo	Lilly
Laboratory tests	X		Early Results Memo	Lilly
Pregnancy test – urine or serum β -HCG	X		Early Results Memo	Lilly
Other baseline physiological assessments	X		Early Results Memo	Lilly
Tumor Imaging -- assessment to support all efficacy analyses (to ensure compliance with SDTM 3.1.3)	X		Early Results Memo	Lilly
If collected, all radiologist reports — including tumor measurements and assessment of response and progression	X		Early Results Memo	Lilly
Adverse events; all safety data	X		Early Results Memo	Lilly
Tumor and Blood Biomarker Assay(s) for exploratory analysis	X		As soon as data is available during final analysis	Lilly
Tumor PD-L1 Biomarker Assay: scoring (including both dose finding cohorts and expansion arms)	X		As soon as possible but no longer than 14 calendar days of the sample receipt	Partner
Tumor PD-L1 Methods and Validation		X ^a	Within 1 month from the date the Tumor PDL-1 Biomarker Assay becomes available in the marketplace	Partner
Durvalumab Immunogenicity (ADA) Data: results	X		As soon as data is available during planned interim and/or final analysis	Partner

Study Procedures	Shared between the Two Parties	Not Shared	Timing to provide item (data/sample, etc.)	Party to Analyze Data/Sample
Durvalumab Immunogenicity (ADA) Data: methods and validation		X ^a	N/A	Partner
Durvalumab PK: results (plasma/serum concentration and PK parameters)	X		As soon as data is available during planned interim and/or final analysis	Partner
Durvalumab PK: methods and validation		X ^a	N/A	Partner
LY2510924 PK: results (plasma/serum concentration and PK parameters)	X		As soon as data is available during planned interim and/or final analysis	Lilly
LY2510924 PK: methods and validation		X ^a	N/A	Lilly

Abbreviations: ADA = antidrug antibody; ECG = electrocardiogram; ECOG = Eastern Cooperative Oncology Group; N/A = not applicable; PD-L1 = programmed cell death ligand 1; PK = pharmacokinetic; SDTM = Study Data Tabulation Model.

- ^a In the event that the Regulatory Authorities require this information to be submitted along with the submission for Regulatory Approval for the use of the Lilly Compound in the Combination, Partner will provide this information directly to the Regulatory Authorities only for such purpose.

Attachment 6. Protocol CXAD Recommendations for Reporting Serious Adverse Events

Recommendations for Reporting Serious Adverse Events

When contacting Lilly to report a SAE, please have the following information available:

Patient Demographics

- patient identification (number), sex, date of birth, origin, height, and weight

Study Identification

- full trial protocol number, investigator's name, investigator's number

Study Drug

- drug code or drug name, unit dose, total daily dose, frequency, route, start dose, cycle details, start date and last dose date (if applicable)

Adverse Event

- description, date of onset, severity, treatment (including hospitalization), action taken with respect to study drug, clinical significance, test and procedure results (if applicable)

Relationship to Study Drug & Protocol Procedures

Concomitant Drug Therapy

- indication, total daily dose, duration of treatment, start date, action taken

In Case of Death

- cause, autopsy finding (if available), date, relationship to study drug and protocol procedures.

Attachment 7. Protocol CXAD ECOG Performance Status

ECOG Performance Status

Activity Status	Description
0	Fully active, able to carry on all pre-disease performance without restriction
1	Restricted in physically strenuous activity but ambulatory and able to carry out performance of a light or sedentary nature, for example, light housework, office work
2	Ambulatory and capable of all self-care but unable to carry out any work activities. Up and about more than 50% of waking hours
3	Capable of only limited self-care, confined to bed or chair more than 50% of waking hours
4	Completely disabled. Cannot carry on any self-care. Totally confined to bed or chair
5	Dead

Source: Oken et al. 1982.

Attachment 8. Protocol CXAD Creatinine Clearance Formula

Serum creatinine CL > 40 mL/min by the Cockcroft-Gault formula (Cockcroft and Gault 1976) or by 24-hour urine collection for determination of creatinine clearance:

Males:

$$\text{Creatinine CL (mL/min)} = \frac{\text{Weight (kg)} \times (140 - \text{Age})}{72 \times \text{serum creatinine (mg/dL)}}$$

Females:

$$\text{Creatinine CL (mL/min)} = \frac{\text{Weight (kg)} \times (140 - \text{Age})}{72 \times \text{serum creatinine (mg/dL)}} \times 0.85$$

Source: Cockcroft and Gault 1976.

Attachment 9. Protocol CXAD Bayesian Model-Based, Toxicity-Band Method for Phase 1a Dose Escalation

The need to minimize the number of patients treated below the biological active dose and the understanding of LY2510924 from earlier nonclinical and clinical studies supports a more efficient dose-escalation design for Study CXAD. Therefore, the Bayesian model-based method is used in this trial to determine the next dose level, based on the predicted probabilities of dose-limiting toxicity (DLT) rates. The exact dose-escalation increment will be determined by the investigators in consultation with collaborator and Lilly CRP or designee and may be different from the model recommendation. This section introduces the background of a model-based dose-escalation method and toxicity-band design (Neuenschwander et al. 2008) and describes the key elements for this trial. Simulation results from the toxicity-band design are presented. These results are also compared with that from the simulation of traditional 3+3 design to demonstrate the benefit of implementing a toxicity-band design in this trial. Fixed and Adaptive Clinical Trial Simulator (FACTS) software version 3.5 is used for all the simulations.

Introduction of CRM-Type Approaches

The Continual Reassessment Method (hereafter, CRM; O'Quigley et al. 1990) is the first Bayesian model-based approach developed for dose-escalation studies. Compared to the traditional 3+3 design that only used current dose level DLT data to estimate the maximum tolerated dose (MTD), CRM utilizes prior dose-toxicity information and all available DLT data to effectively estimate the MTD. To improve the operating characteristics of CRM, Goodman et al. (1995), among others, have proposed modified-CRM (MCRM) procedures to make the model-based designs more acceptable in practice. The major modifications include:

- Always start at the lowest dose level.
- Limit the escalation increment.
- Escalate by cohorts rather than single patients.

Babb et al. (1998) proposed the Escalation with Overdose Control (EWOC) method that directly controls the probability of overdosing during dose escalation. EWOC is also a CRM-type method. During the escalation, EWOC selects the next dose such that the predicted probability that the new dose exceeds the MTD is equal to a prespecified feasibility bound $\alpha=0.25$. The connection between CRM and EWOC is that CRM typically uses the middle (mean or median) of the MTD's posterior distribution as the next recommended dose, whereas EWOC uses the 25th percentile. Therefore, EWOC is a more conservative method than the original CRM method.

Toxicity-Band Design

Neuenschwander et al. (2008) extended the concept of EWOC (Babb et al. 1998) and proposed considering the uncertainty of the posterior distributions and using interval estimates to make the dose recommendation, herein referred to as the toxicity-band design.

The Model

A two-parameter logistic model is used to model the relationship between dose and probability of a DLT:

$$\text{logit}\{p(d)\} = \alpha + \beta \log\left(\frac{d}{d^*}\right), \quad \beta > 0. \quad (1.1)$$

In the model, d is the true dose and $p(d)$ is the probability of a DLT at dose d . d^* is the reference dose such that α is interpreted as the log-odds of a DLT at d^* .

Toxicity Band

The probability of a DLT is categorized to 4 bands:

- Underdosing: $p(d)$ in $(0, 0.20]$
- Targeted toxicity: $p(d)$ in $(0.20, 0.33]$
- Excessive toxicity: $p(d)$ in $(0.33, 0.60]$
- Unacceptable toxicity: $p(d)$ in $(0.60, 1.00]$

Overdosing is defined as $p(d) > 0.33$.

Dose Recommendation

During the escalation, after each cohort of patients, we

1. Calculate the posterior probabilities of the 4 toxicity bands, for each dose.
2. Exclude the doses such that the posterior probabilities of overdosing are larger than 0.25 (overdosing control criteria). The remaining doses are the ones that satisfy the overdose control criteria.
3. Among the remaining doses, the dose with the highest posterior probability in the targeted toxicity band will be the model recommendation of the next dose.

The data will be evaluated on an ongoing basis until the MTD is determined. Once the MTD has been identified, a discussion between the sponsor and investigators may occur in order to treat additional patients at intermediate doses below the MTD.

Dose Range and Reference Dose

Assuming that the starting dose level is 20 mg, based on the preclinical data, the highest dose level that will be explored in this study is 40 mg and the reference dose in model (1.1) is chosen as $d^* = 40$ mg.

The Prior Distribution on Model Parameters

A Quantile-based uninformative prior (Neuenschwander et al. 2008) is used to derive a bivariate-normal prior on $(\alpha, \log\beta)$. Based on preclinical experience of LY2510924, the prior median probability of DLT for the dose levels was determined as in Table App.1. Any intermediate dose level within the starting doses to 40 mg can be explored.

Table App.1. Prior Median Probability of Dose Limiting Toxicity at Each Dose Level

Dose (mg)	Median Probability of Dose Limiting Toxicity
10	0.06
20	0.12
30	0.18
40	0.26

For each dose, the minimally informative unimode Beta distribution (a,b) is derived as the prior distribution for the probability of DLT, so that the operating characteristics of the model are robust to the selected prior distribution of DLT:

- For median probability of DLT <0.5 , $b=1$ and $a(<1)$ are tuned to match the median.
- For median probability of DLT >0.5 , $a=1$ and $b(<1)$ are tuned to match the median.

Figure App.1 shows the median and the 95% confidence interval (CI) of the prior distribution of the DLT rate at each dose level.

[figure not shown]

Figure App.1. The prior distribution of the dose limiting toxicity rate at each dose level.

A bivariate normal distribution was derived on $(\alpha, \log\beta)$ that stochastically gives the best fit to the 2.5%, 50%, and 97.5% quantiles of the prior probability of DLT at each dose. The parameters $(\alpha, \log\beta)$ have a bivariate normal distribution with mean= $(-1.09, 0.26)$, standard deviation= $(2.17, 0.51)$, and $\rho=-0.89$.

Simulation Studies

We performed simulations under different scenarios of possible dose-toxicity relationships to investigate the operational characteristics of the toxicity band versus traditional 3+3 design:

- 3-patient cohorts starting from 20 mg.
- Maximum number of patients: 15 for toxicity-band method, and 15 for traditional 3+3 method.
- Rules for stopping early for toxicity-band method: at least 6 patients have been treated at or near MTD or the probability of dose being in target band greater than 0.5 or at least 9 patients have been accrued.

Four scenarios were considered to represent a wide range of possible dose-toxicity relationships as shown in Figure App.2 and Table App.2. DLT rates for the starting dose level are chosen to take into account single patient cohorts before the true DLT rate of the MTD is set at 20~33% across scenarios. Scenarios 1, 2 and 3 have MTD at 40 mg, and Scenario 4 has the MTD at 30 mg. When the dose-toxicity curve is steep around MTD, the concern is the risk of overdosing; when the dose-toxicity curve is flat around MTD, the concern is underdosing. The simulation studies will assess the performance of the toxicity-band method and compare it to the traditional 3+3 focusing on these concerns.

[figure not shown]

Figure App.2. The dose-toxicity relationships under each scenario.

Table App.2. The Dose-Toxicity Relationships

Dose (mg)	Scenarios			
	1	2	3	4
10	0.05	0.06	0.07	0.07
20	0.09	0.12	0.15	0.18
30	0.14	0.19	0.24	0.29
40	0.22	0.27	0.33	0.42

1000 simulations were conducted under each scenario to investigate the operational characteristics of toxicity-band and traditional 3+3 methods. The results are summarized in Table App.3.

Table App.3. Comparison of Toxicity-Band and Traditional 3+3 Method

	Scenario 1		Scenario 2		Scenario 3		Scenario 4	
	TB	3+3	TB	3+3	TB	3+3	TB	3+3
Rate of Selected as MTD for Each Dose (mg/kg)								
10 mg +durvalumab	0.064	0.087	0.121	0.14	0.196	0.175	0.253	0.24
20 mg + durvalumab	0.083	0.157	0.139	0.219	0.21	0.315	0.276	0.371
30 mg + durvalumab	0.164	0.227	0.194	0.276	0.22	0.265	0.249	0.262
40 mg + durvalumab	0.689	0.529	0.546	0.365	0.374	0.245	0.222	0.127
Rate of selecting Ph2 Dose below true MTD	0.311	0.471	0.454	0.635	0.626	0.755	0.529	0.611
Rate of selecting Ph2 Dose above true MTD	--	--	--	--	--	--	0.222	0.127
Rate of DLT events during the trial	0.164	0.165	0.199	0.211	0.240	0.259	0.270	0.302
Mean # Patients	14.5	10.4	14.1	10.1	13.6	9.6	13.2	9.0
Mean # Patients at true MTD	4.7	3.1	3.7	2.7	3.1	2.2	3.4	3.2

Abbreviations: DLT = dose-limiting toxicity; MTD = maximum tolerated dose; Ph2 = Phase 2.

The traditional 3+3 design is generally conservative and has a higher rate of selecting a dose level below the true MTD to be recommended for future Phase 2 studies, increasing the risk of underdosing and failure rate of Phase 2 studies. The toxicity-band method is slightly more aggressive in general and has a lower rate of MTD selection below the true level, and a higher rate of MTD selection at the true level. The mean percentages of a DLT event in each scenario are in general higher in 3+3 method, but strictly kept below the prespecified overdosing control criterion at 0.25.

Examples

Examples from Scenario 1 and Scenario 4 are provided here to illustrate how the toxicity-band method operates under certain circumstances.

Example 1

Scenario 2 has a true MTD at 40 mg with a DLT rate of 0.27 in Table App.2. With a slowly increasing relationship between the dose level and the DLT rate, patients could be assigned to dose levels under MTD and cause underdosing when DLT occurs in the first few cohorts.

With the toxicity-band method, the next recommended dose level is 40 mg after the 12th patient is treated (Figure App.3), although 2 DLTs are observed at 40 mg, and 40 mg will be declared as MTD after the 15th patient. The toxicity-band method is able to allocate more patients at the MTD dose level.

[figure not shown]

Figure App.3. A case study for Scenario 2.

Example 2

Scenario 4 has a true MTD at 30 mg with a DLT rate of 0.29 in Table App.2. With a relatively steep increasing relationship between the dose level and the DLT rate, patients could be assigned to dose levels under MTD and cause underdosing when DLT occurs in the first few cohorts.

With the toxicity-band method, the next recommended dose level is still 30 mg after the 9th patient is treated (Figure App.4), although 2 DLTs are observed at 30 mg, and 30 mg will be declared as MTD after the 15th patient, even though there are 3 DLTs observed. The toxicity-band method has also allocated more patients at the MTD dose level.

[figure not shown]

Figure App.4. A case study for Scenario 4.

Summary

As a conclusion, based on the simulation studies on a variety of scenarios and the illustrative examples, the toxicity-band method is slightly more aggressive than the traditional 3+3 design, and therefore provides a lower underdosing rate and a higher MTD selection rate, with a well-controlled overdosing rate at a prespecified criterion. Therefore, the modified 3+3 method that incorporates the principles of the toxicity-band method will be used in this study rather than the traditional 3+3 escalation paradigm.

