7.2.2. Phase 1a Dose Escalation

The MTD of LY2510924 determined during Phase 1a will be used for Phase 1b.

Three dose levels will be investigated in Phase 1a ([Figure CXAD.6.1](#)). Dose escalation is described in Section [7.2.2.2](#).

Because Phase 1a is the dose-escalation part of the study, data will be evaluated on an ongoing basis until the MTD is determined. Safety data, in particular AEs, will be the primary criteria for the dose escalation. No dose escalation can occur without prior discussion and agreement between the investigator and the Lilly study team in consultation with the collaborator.

No inpatient dose escalation or reduction is allowed during Phase 1a.

Dose escalation will be based on the number of DLTs experienced during Cycle 1.

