7.2.2.2. Dose-Escalation Method

Adaptive scheme, with incorporation of a Bayesian model-based, toxicity-band method (Neuenschwander et al. 2008), will be used to assess the safety of LY2510924 given in combination with durvalumab. The Bayesian model-based, toxicity-band method incorporates the prior expectations of the dose-toxicity curve and the observed DLT data after each cohort and provides quantitative guidance on the determination of the dose level for the next cohort. The dose recommendation relies on maximizing the probability of targeted toxicity while controlling the probability of excessive or unacceptable toxicity. This method will be applied to the observed data on an ongoing basis throughout the dose escalation. The toxicity-band method will stop early if the prespecified maximum number of patients is reached or the recommended next dose level has been administered to at least 6 patients.

During the dose-escalation period, the investigators and Lilly CRP or designee in consultation with collaborator will consider the model recommendation, the observed DLT rate, and any

DLT-equivalent toxicities observed in Cycle 2 and beyond at each cohort to determine the next dose level and determine when to stop dose escalation. Safety data, in particular, DLTs, will be the primary criteria for dose escalation. In addition, if available at the time of the dose-escalation decision, PK results will be used as secondary/supporting data for dose escalation. Additional patients may, therefore, be enrolled at a specific dose level to characterize PK/pharmacodynamics. No dose escalation can occur without prior discussion and agreement between the investigator and the Lilly CRP or designee in consultation with collaborator; the decision will be documented in writing.

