The dose levels for dose escalation are provided in [Figure CXAD.6.1](#). The starting dose level will be 20 mg. The 20-mg and 30-mg dose levels will enroll 3 patients initially. The 40-mg dose level will enroll and treat 1 patient initially. After a 2-week observation period, the additional patients will be enrolled after notification from the sponsor. For all dose levels after the initial 3 patients have been enrolled, additional patients (at that dose level) may be enrolled in case of DLT. If deemed necessary, additional dose levels may be explored after discussion between the investigator and the Lilly CRP or designee in consultation with collaborator. The toxicity-band method has the ability to accommodate additional dose levels naturally. The DLT observation period will last for 4 weeks or to the completion of Cycle 1. Additional patients will be enrolled in a cohort to achieve the minimum of 3 evaluable patients if dropouts or dose interruptions occur that result in a patient being nonevaluable for DLTs due to nonmedical reasons. Patients who withdraw from the study during the DLT observation period for reasons other than a DLT may be replaced within the same dose level. For the purpose of making decisions on dose escalation from a safety perspective, patients will be considered evaluable (DLT-evaluable population) if they have either completed the DLT-observation period (Cycle 1) and received the scheduled durvalumab dose and at least 75% of LY2510924 doses in Cycle 1 or have discontinued study treatment or study participation before completing Cycle 1 due to a DLT. If the DLT-observation period is extended to Cycle 2, patients who discontinued during Cycle 2 in the absence of DLT-equivalent toxicity will be considered evaluable for DLT assessment.

Details regarding the toxicity-band method for this study are provided in [Attachment 9](#).

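### One DLT in the first three patients makes the overdose rule exclude every planned dose with no stated fallback, and Table App.3 simulates a design other than the one written

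*Protocol*

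**What the plan says.** **Dose rule.** Attachment 9 (Dose Recommendation) computes posterior toxicity-band probabilities after each cohort. Its second step is to "Exclude the doses such that the posterior probabilities of overdosing are larger than 0.25 (overdosing control criteria", where overdosing means a DLT probability above 0.33. The third step takes, from the doses left, the one most likely to lie in the target band. Nothing covers the case where none is left. The introduction to Attachment 9 says that the increment actually used "may be different from the model recommendation", and intermediate doses are allowed only from the starting dose up to 40 mg.

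**Dose set.** Section 7.2.2 states "Three dose levels will be investigated in Phase 1a". The text elsewhere names 20, 30 and 40 mg, starting at 20 mg. Section 7.2.2.2 adds that "additional patients (at that dose level) may be enrolled in case of DLT" and "If deemed necessary, additional dose levels may be explored after discussion". There the team weighs the model, the observed DLT rate and later toxicities "to determine the next dose level and determine when to stop dose escalation".

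**Stopping.** Section 7.2.2.2 stops at the maximum number of patients or when "the recommended next dose level has been administered to at least 6 patients". The Simulation Studies part of Attachment 9 lists different early stops: six patients at or near the MTD, or "the probability of dose being in target band greater than 0.5 or at least 9 patients have been accrued".

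**Performance.** Table App.3 gives selection rates for 10, 20, 30 and 40 mg. Sections 6.2 and 10.1, the Attachment 9 summary and SAP Section 5 claim less underdosing and more frequent MTD selection than 3+3.

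**The concern.** Identifying the MTD is the Phase 1a primary objective, and a single DLT among the first three patients is an ordinary event. If the overdose rule then rejects every planned dose while the main text allows expansion at 20 mg, the written safeguard and the written practice point in different directions at the first likely decision. Separately, the performance figures are the stated reason for preferring this method to 3+3. If they come from another dose set and stopping rule, they do not show how the written design performs, or how often it would leave no admissible dose.

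**Working it through.** **Inputs (Attachment 9).** Model: logit p(d) = α + β·log(d/40). Prior on (α, log β): bivariate normal, mean (−1.09, 0.26), SD (2.17, 0.51), ρ = −0.89. Limit: P(p > 0.33) at most 0.25. True DLT rates at 20 mg (Table App.2): 0.09, 0.12, 0.15, 0.18.

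**1. Reproduce the plan's prior.** Integrating the prior over a grid gives median DLT rates of 0.05/0.12/0.19/0.25 at 10/20/30/40 mg. Table App.1 has 0.06/0.12/0.18/0.26.

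**2. Posterior after 1 DLT in 3 at 20 mg.** The posterior is proportional to prior × p(20)·(1 − p(20))².

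| Dose (mg) | P(p > 0.33) |
|---|---|
| 10 | 0.195 |
| 20 | 0.38 |
| 25 | 0.46 |
| 30 | 0.53 |
| 40 | 0.65 |

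The 0.25 limit is crossed at about 12.8 mg, so everything from 20 to 40 mg fails. Rounding in the printed prior does not matter: moving all five parameters by ±0.005 leaves 20 mg at 0.379 to 0.382.

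**3. How often.** P(exactly 1 of 3) = 3π(1 − π)²:
- Scenario 1: 3 × 0.09 × 0.91² = 22.4%
- Scenario 2: 3 × 0.12 × 0.88² = 27.9%
- Scenario 3: 3 × 0.15 × 0.85² = 32.5%
- Scenario 4: 3 × 0.18 × 0.82² = 36.3%

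**4. Which rule produced Table App.3?** All paths were enumerated exactly on 10/20/30/40 mg: three-patient cohorts, start at 20 mg, no skipping, maximum 15, and a stop when no dose passes.

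| Early stop | Mean N, Scenarios 1–4 |
|---|---|
| Printed table | 14.5 / 14.1 / 13.6 / 13.2 |
| Nine accrued, read literally | at most 9 |
| Six patients at recommended dose (7.2.2.2) | 12.4 / 12.0 / 11.6 / 11.2 |
| Only when no dose passes | 14.4 / 14.0 / 13.6 / 13.2 |

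The last row fits, but the protocol never states that rule.

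**5. The missing outcome.** The selection rates sum to 1.000 in all eight columns (for example 0.064 + 0.083 + 0.164 + 0.689). In the run that fits:

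| | Sc. 1 | Sc. 2 | Sc. 3 | Sc. 4 |
|---|---|---|---|---|
| No dose admissible, % | 5.7 | 9.4 | 13.7 | 17.7 |
| 10 mg selected, % | 1.2 | 2.9 | 5.6 | 8.9 |
| Sum, % | 6.9 | 12.3 | 19.3 | 26.6 |
| Printed 10-mg row, % | 6.4 | 12.1 | 19.6 | 25.3 |

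With 1000 runs, the simulation standard error of the printed row is √(0.064 × 0.936/1000) = 0.8 points in Scenario 1 and √(0.253 × 0.747/1000) = 1.4 points in Scenario 4. The sum agrees with the printed row; 10 mg alone does not.

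**6. The written dose set.** Same enumeration on 20/30/40 mg only, with the six-patient rule and the model followed literally:

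| | Sc. 1 | Sc. 2 | Sc. 3 | Sc. 4 |
|---|---|---|---|---|
| True MTD selected, % | 56.2 | 40.6 | 26.9 | 19.7 |
| No dose admissible, % | 30.0 | 40.8 | 51.5 | 61.6 |
| Printed toxicity band, true MTD, % | 68.9 | 54.6 | 37.4 | 24.9 |
| Printed 3+3, true MTD, % | 52.9 | 36.5 | 24.5 | 26.2 |

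The printed margins over 3+3 are +16.0, +18.1, +12.9 and −1.3 points. On this run they become +3.3, +4.1, +2.4 and −6.5. The dose set matters more than the stopping rule: with four doses and the six-patient rule, true-MTD selection is 68.6/52.4/36.9/28.4%.

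If 25 mg is opened (DLT rate assumed midway between 20 and 30 mg) and one override at 20 mg is allowed after 1/3, 40 mg is selected in 67–71/50–54/34–37% of trials in Scenarios 1–3. No dose is admissible in 13–14/22–24/33–35/45–46% in Scenarios 1–4.

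**The case against.** The model is guidance. Its recommendation may be overridden, expansion at 20 mg after a DLT is expressly permitted, and further levels may be opened after discussion. A reader might infer from step 2 that the trial deadlocks or that no next step exists. The documents do not support that. What is left is narrower: none of these provisions gives a trigger or names a lower dose, and using the expansion means setting the overdose limit aside.

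Attachment 9 itself models 10 mg, which passes at 0.195, so the set is not empty on that grid. True, but the text of the plan does not list 10 mg as a Phase 1a level. The dose-level figure is not available here, so a lower level drawn there cannot be excluded.

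Before any data, 20 mg already stands at 0.305. That is not a breach: step 2 applies after each cohort and 20 mg is the fixed start.

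The mean sample sizes could reflect a wording slip. If the listed early stops were meant to apply jointly, the enumeration again gives 14.4/14.0/13.6/13.2, because the joint condition never triggers within 15 patients. This stands. The mismatch with the literal wording is certain, but its cause is not.

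Pooling no-dose trials under 10 mg would not flatter the method, since they would count as selections below the true MTD. That also stands.

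Finally, a reader might infer that the claimed advantage over 3+3 is unsupported. That goes too far. Even the literal three-dose run stays above the printed 3+3 rates in Scenarios 1–3. Counting every no-dose trial as underdosing gives 44/59/73% against 47.1/63.5/75.5% for 3+3.

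**Conclusion.** The point holds as a should-fix item. After 1 DLT in 3 at 20 mg, an event with probability 22% to 36% in the sponsor's scenarios, the printed prior makes the overdose rule exclude every dose from 20 to 40 mg, and Attachment 9 has no action for that case. Table App.3 does not describe the written design in its dose set, its stopping rule or its list of outcomes.

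The advantage over 3+3 in Scenarios 1–3 probably survives in direction but is smaller than printed, about 2 to 4 points if the model is followed literally on three doses. That comparison is imperfect, because the printed 3+3 figures come from the table that includes 10 mg. In Scenario 4 the printed table already favours 3+3 (24.9% against 26.2%).

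The posterior figures rest only on the printed model and prior. The selection and no-dose rates also depend on assumptions about overrides and intermediate doses, so the 30% to 62% without an admissible dose is not the design's fixed performance. That no-dose trials were counted under 10 mg is an inference, because the simulation settings are not shown.

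**What to change.** - State one dose set in Sections 7.2.2 and 7.2.2.2 and Attachment 9, with 10 mg in or out and intermediate doses in or out. This has consequences: after 1/6 at 20 mg, 30 mg fails narrowly (0.254) but 25 mg passes (0.186).
- State one stopping rule in Section 7.2.2.2 and Attachment 9, and correct the nine-patient line.
- State the action when no planned dose passes. One option is three more patients at 20 mg after 1/3: continue at 1/6 (20 mg passes at 0.12), stop or de-escalate at 2/6 (0.41). Another is to de-escalate to 10 mg (0.195); after 0/3 there, 20 mg passes again at 0.18.
- Re-run both the toxicity-band and the 3+3 simulations on that dose set, with a separate row for trials in which no dose is admissible.
- Restate Table App.3 and the comparative claims in Sections 6.2 and 10.1, Attachment 9 and SAP Section 5.

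The cost is a few hours of simulation and wording. The maximum of 15 patients stays, and the SAP 5.1 statement that the mean is at most 15 remains true. The downside is that the stated gain over 3+3 may be smaller.
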